### **5.2.5 Tissue processing**

For the primary goal, immediately after tumor resection, the OxyChip will be removed from the tissue and inspected visually to confirm that the device remained intact. The tissue at the site of the OxyChip will be submitted for processing with standard DHMC pathology procedures. Tissue sections spanning the OxyChip placement site will be stained with hematoxylin and eosin and evaluated for the presence of acute or chronic inflammation or other tissue reaction (scar, fibrosis, capsule formation, or other). After removal from the tissue, the OxyChip will be recalibrated to confirm that there was no change in the oxygen sensitivity during the course of the implantation. The pathologist, the PI, or a co-investigator who is present during specimen dissection will note if the OxyChip has been damaged during the extraction. Details in standard method 70.x.

If the OxyChip cannot be identified in the surgical specimen by dissection, the specimen will be subjected to MRI, ultrasound, or EPR analysis to visualize the OxyChip, which will facilitate the dissection.

For the exploratory goals, this tissue will be examined or stored for expression of biomarkers that may be associated with hypoxia or tumor growth.

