### **1.6.3 Rationale for the option of implanting fiducials with the OxyChip**

[figure not shown]
In order to assist with locating the OxyChip during treatment, during EPR measurements, and during/after resection, the protocol was revised to allow for fiducial(s) (either one or two) to be implanted along with the OxyChip during the procedure. The decision to implant fiducials is at the discretion of the investigator.

Because tumors size and shape can change during the course of radiation, the location of the OxyChip in relationship to the tumor may also change. By implanting fiducials with the OxyChip, the location of the OxyChip will be able to be seen on CT scans that patients intermittently receive during radiation treatment as part of clinical care. This will allow for better interpretation of the pO2 measurements that are collected throughout the treatment, as the location of the OxyChip in relation to tumor tissue will be evaluable.

Adding fiducials will also assist in locating the OxyChip for EPR measurements. Although OxyChips can be located *in vivo* using ultrasound guidance, it can be challenging to do so; fiducials can be located quicker than the OxyChip implanted alone and with higher sensitivity. This allows for faster placement of the resonator, which facilitates faster oxygen measurements. This is of great importance in the clinical translation of EPR oximetry, where time is limited.

Fiducials will also assist in procedures during and after resection. In order to assure that the OxyChip has been explanted, the pathology specimen will be scanned prior to surgical closure in the pathology lab. If the implanted fiducial(s) are located in the resected specimen, then there is high confidence that the OxyChip has been successfully explanted (See section 5.2.4 for more information on this procedure). Fiducials can also assist with assessing the pathology specimen after resection to ensure that the OxyChip is not cut during the dissection of the specimen, and to rapidly identify the location of the OxyChip in the specimen. If two fiducials are implanted, the orientation of the OxyChip will be known, so the pathologist will cut parallel to the two fiducials in order to not cut the OxyChip in the process.

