## 2 Study Objectives

### 2.1 Primary Objective

This is a safety study to demonstrate that the implantation procedure, the OxyChip, and any subsequent oxygen measurements will be well-tolerated by the patient with minimal risk for complications. Specific adverse effects that will be monitored include:

- Allergic reactions or signs of inflammation at the site of implantation or systemically
- Infection at the site of implantation
- Bleeding at the site of implantation
- All tumors will be excised with the OxyChip in place, and histology will be analyzed for signs of tissue reaction and inflammation adjacent to the OxyChip
- Device (PDMS-embedded) breakage, loss of EPR or oxygen sensitivity, or change of calibration
- Erosion of skin over the implantation site
- Any unanticipated adverse device effects (UADE) will be assessed and reported. UADE will be defined as, “any serious adverse effect on health or safety or any life-threatening problem or death caused by, or associated with, a device, if that effect, problem, or death was not previously identified in nature, severity, or degree of incidence in the investigational plan or application, or any other unanticipated serious problem associated with a device that relates to the rights, safety, or welfare of subjects” (21 CFR 812.3(s)).

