### 2.2 Secondary Objective

This study will also determine the feasibility of repeated measurements of oxygen in tumors using the OxyChip and EPR oximetry. This objective is unrelated to the primary safety objective.

- To assess the feasibility of making repeated measurements of tumor oxygen levels in patients with easily-accessible, superficial tumors.
- To determine the tumor oxygen levels in patients without therapy prior to surgical excision (Phase 1A), or during a course of radiotherapy or neoadjuvant chemotherapy prior to surgical excision (Phase 1B).
- To determine the workflow and time required for each daily oxygen measurement.

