This larger cohort will allow further assessment of safety, as well as optimization of procedures for the OxyChip placement and subsequent oxygen measurements for different tumor types in different anatomical locations. This expanded Phase 1 study will also achieve a secondary goal of increasing patient numbers for specific tumor types (*i.e.*, melanomas, squamous cell carcinomas and sarcomas) to assess the levels of tumor oxygenation and their response to supplemental oxygen breathing.

The phase 1B patients will have up to five oxygen measurements per week during the course of radiation or chemotherapy. Patients will be evaluated weekly during radiotherapy or prior to each chemotherapy administration or follow-up appointment for assessment of any adverse effects, as per the primary objective. Oximetry measurements will be taken periodically, from at least one day after implantation up to the OxyChip's removal. The OxyChip will be removed at a planned surgery as part of standard-of-care therapy. Phase 1A patients will be evaluated at least monthly prior to OxyChip removal for assessment of adverse effects, again for the primary objective.

If a patient cannot or does not return for an evaluation, the study team will contact the patient by phone or email to check for development of new adverse events or changes in health status. Assessments by non-study physicians or physician extenders as part of standard care are also an acceptable replacement, if the patient is not accessible for an in-person evaluation. Following resection, the tissue surrounding the OxyChip will be examined for any adverse effects, as per the primary objective. For the exploratory objectives, the tissue will also be examined for biomarkers associated with hypoxia or growth.

Schema:

PHASE 1A	
Purpose	
Primary: Safety of the OxyChip placement procedure and OxyChip removal after short duration (typically less than 4 weeks, but up to 52 weeks).
 
Secondary: Feasibility of taking repeated oxygen measurements using the OxyChip.

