## 5.2 Treatment Regimen

### 5.2.1 OxyChip and fiducial placement

Fiducial(s) (one or two) may be implanted along with the OxyChip during the procedure at the discretion of the investigator. It is anticipated that fiducials will be used in most tumors, excepting those where superficiality and expected ease of OxyChip assessment make their use sub-optimal (for example for a, fungating skin tumor where the OxyChip is placed < 1 cm from the surface). Placement of the OxyChip and fiducials (if implanted) will occur via a **collaborative effort between the surgical oncologist and the PI or one of the co-investigators** with the following goals and protocol:

- (i) The OxyChip and fiducials will need to be removed in their entirety when the tumor is resected.
- (ii) The OxyChip will be positioned within the tumor and within 3 cm of the skin or mucosal surface.
- (iii) The selection of the specific site for insertion is guided (by available pre-operative MRI, CT, or PET imaging, or physical exam) to be inside the viable tumor and not in a necrotic core. All implantations will be performed with sterile technique with the skin prepped with alcohol or betadine and draped in a sterile fashion. The OxyChip and fiducials will be implanted by a minimally invasive, needle-based approach. The needle will be loaded by the provider injecting the OxyChip in the following order depending on what is determined to be implanted. Loading occurs immediately prior to implantation, in the sterile field:
  - a. OxyChip only: The needle is loaded with a single OxyChip.
  - b. One fiducial and OxyChip: The needle is loaded with both the fiducial and single OxyChip. Order within the needle for implantation is not significant; therefore, the fiducial may be loaded first into the needle and then the OxyChip or vice versa.
  - c. Two fiducials and OxyChip: The needle is loaded in the following order: one fiducial, the single OxyChip, then one fiducial.
- (iv) A local anesthetic will be offered to all patients prior to the implantation. After numbing, the loaded needle will be placed in the tumor guided by palpation (if sufficiently superficial and large), ultrasound, or a CT-guided procedure, and the needle contents will be deployed into the tumor using a stylet (Figure 6). The placement of the OxyChip may be performed by protocol trained Radiology staff or by protocol trained study personnel.

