# 7 Statistical Plan

## 7.1 Statistical Methods

This is a first-in-humans pilot study/Phase I trial designed to (1) test the safety and toxicity of the OxyChip and patient tolerance of its presence and to (2) help design a larger confirmatory study. As such, the study was sequentially designed into different cohorts, as previously described in section\_3.1. The criteria for proceeding with each cohort is not based on statistical significance but on the presence and severity of any unexpected adverse events and whether they can be attributed to the OxyChip. The sample size was selected to be within the range recommended for early phase I trials.

For purposes of examining the secondary goal, the feasibility of using the OxyChip to assess PO2, we will use a qualitative assessment about whether any attempted measurements were successful, and assess the time for making measurements. Oxygen measurements will be averaged across visit days (if available) per subject for all subjects in Phase 1A and Phase 1B. We will use a paired t-test to detect statistically significant acute changes in pO2. To compare time period measurements per visit across patients, we will use an ANOVA model to account for individual variation of the baseline pO2. Finally, if the oxygen level exhibits a nonlinear pattern we will use a nonlinear fitting technique. To account for substantial variations of pO2 across patients, methods of repeated measurements and mixed modeling will be used.

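### No recorded tissue read or analysis rule checks that the chip lay in viable tumour, so an off-target pO2 would be summarised as tumour oxygen

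*Combined protocol and SAP*

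**What the plan says.** The pO2 objective in section 2.2 concerns tumour: "To determine the tumor oxygen levels in patients without therapy prior to surgical excision (Phase 1A"), and likewise during radiotherapy or neoadjuvant chemotherapy in Phase 1B. Section 5.2.1(iii) selects the insertion site "to be inside the viable tumor and not in a necrotic core". Section 1.6.3 accepts that this may not last: "Because tumors size and shape can change during the course of radiation, the location of the OxyChip in relationship to the tumor may also change". It offers fiducials seen on clinical CT during radiation as an aid to interpretation, "as the location of the OxyChip in relation to tumor tissue will be evaluable".

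Wherever the protocol describes the chip-site tissue read, the purpose is safety. Section 2.1 says that "histology will be analyzed for signs of tissue reaction and inflammation adjacent to the OxyChip". Section 3.1 says "Following resection, the tissue surrounding the OxyChip will be examined for any adverse effects, as per the primary objective". Section 5.2.5 has the H&E sections "evaluated for the presence of acute or chronic inflammation or other tissue reaction (scar, fibrosis, capsule formation, or other". Tissue is also kept for exploratory biomarkers.

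On analysis, section 7.1 says "Oxygen measurements will be averaged across visit days (if available) per subject for all subjects in Phase 1A and Phase 1B". Section 3.1 defines an evaluable patient only by at least 3 days of implantation, and section 7.2 analyses all evaluable participants.

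**The concern.** The protocol treats chip position as material to the measurement: it sets a target at insertion and acknowledges that position relative to tumour can change. It also cuts sections through the site. Yet the read described does not ask what tissue surrounded the chip, and no analysis step uses position. A chip in necrosis, in a treated bed or in normal tissue would contribute a value carrying the same label as one in viable tumour.

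What is at stake is the secondary pO2 description and its later use. Section 1.6.1 wants baseline pO2 and oxygen responsiveness by tumour type, and a better power calculation for a later pivotal or therapeutic trial. Off-target values would alter both the mean and the between-patient spread that such a calculation draws on.

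**Working it through.** The plan gives no misplacement rate and no expected pO2, so there is no figure of its own to reproduce. The check has three parts.

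**1. Does any step link tissue type to pO2?**
- Insertion (5.2.1): a target, pursued by palpation if the tumour is sufficiently superficial and large, or by ultrasound or CT. This is aim, not confirmation.
- During therapy (1.6.3): CT localisation depends on fiducials, which are at the investigator's discretion, and on clinical scans during radiation. Section 5.2.2 allows ultrasound to find the chip, in order to place the resonator.
- At removal (5.2.4): fiducial imaging before surgery and fluoroscopy of the specimen serve retrieval.
- Histology (2.1, 3.1, 5.2.5): inflammation, tissue reaction and adverse effects. Scar and fibrosis are noted, but as reactions.
- Analysis (3.1, 7.1, 7.2): neither the definition of evaluable nor the averaging, paired t-test, ANOVA or mixed model carries a location term or condition.

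No step in the text available makes the link.

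**2. Could an off-target value be spotted from the number alone?** Section 1.5.6 reports human OxyChip baselines from about 1 mmHg (SCC) to about 24 mmHg (lipoma). Mouse muscle in section 1.3.14 averages 15.6 mmHg, inside that range. So the reading by itself would not identify a chip in non-tumour tissue.

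**3. Illustration of size.** Let f be the share of chips off target, t the mean pO2 in viable tumour and m the mean at off-target sites.
- Chance of at least one off-target chip among n: 1 - (1 - f)^n, with n = 30 (one phase) or 60 (total).
- Shift in the mean: (1 - f)t + fm - t = f(m - t).
- Assumed f: 5%, 10%, 20%.
- Assumed t: 5 mmHg (middle of the 0 to 10 mmHg India-ink range, section 1.4) or 12.5 mmHg (middle of the 1 to 24 mmHg OxyChip range, section 1.5.6).
- Assumed m: 0 mmHg for necrosis, or 15.6 mmHg (mouse muscle).

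| f | At least one of 30 | At least one of 60 | t=5, m=0 | t=5, m=15.6 | t=12.5, m=0 | t=12.5, m=15.6 |
|---|---|---|---|---|---|---|
| 5% | 78.5% | 95.4% | -0.25 | +0.53 | -0.63 | +0.16 |
| 10% | 95.8% | 99.8% | -0.50 | +1.06 | -1.25 | +0.31 |
| 20% | 99.9% | >99.9% | -1.00 | +2.12 | -2.50 | +0.62 |

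Shifts are in mmHg. For example, at f = 10%: 0.10 x (15.6 - 5) = +1.06, and 0.10 x (0 - 12.5) = -1.25. The sign depends on m and the size on every input, so the table bounds nothing. It shows only that modest rates would make at least one such chip likely, and that the net effect on a mean could go either way.

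**The case against.** **Existing controls.** Tumours must be at least 2.5 cm in minimum diameter (4.1), against a chip 0.6 mm wide and 3 to 5 mm long (1.2). Section 5.2.1 anticipates fiducials in most tumours, and section 5.2.4 images them around surgery in either phase. These lower the risk of a miss and stand as mitigation. None enters an analysis rule.

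**Unseen text.** Section 5.2.5 defers detail to standard method 70.x, its list of reactions is open-ended, and the study PI reviews surgical pathology reports before cohorts expand (3.1). Tissue type may therefore be recorded somewhere. That stands, and limits the claim to what the text available says. Even if it is recorded, section 7.1 does not use it.

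**Spatial resolution.** Section 1.3.2 argues that resolving heterogeneity within a tumour is unnecessary. That presumes a sensor in tumour and refers to monitoring at several sites, whereas section 5.2.1 loads a single OxyChip per implantation. It does not answer this point.

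**Stronger readings.** A reader might infer that misplaced chips have already distorted the pO2 results, or that the bias is upward by 1 to 3 mmHg. The documents report no off-target chip, and the upward figure needs tumour at 5 mmHg together with muscle-like off-target tissue; other inputs shrink or reverse it. A reader might also conclude that both phases should be restricted to chips found in tumour at resection. In Phase 1B that would be a mistake. The specimen follows therapy (section 5.2.4 expects at least 5 weeks of implantation), so necrosis or fibrosis at the site does not show that earlier sessions were off target. Excluding those patients would select on response and could discard valid pre-treatment sessions.

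**Conclusion.** The gap is real but confined to the secondary pO2 results. On the text available, the chip-site histology is read for safety only, and pO2 is summarised for all subjects without regard to the tissue the chip lay in. An off-target reading, if one occurred, would be reported as tumour oxygen and carried into planning for a later trial, and the reader could not tell.

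Size and direction are unknown; the illustration rests wholly on assumed rates and values. The primary endpoint (grade 3 or higher toxicity attributed to device or procedure, section 3.2) and the secondary endpoint of completing planned measurements (section 3.3) do not depend on chip location. The change is worth making because the slides are already being read and no new procedure is needed.

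**What to change.** **Section 5.2.5.** Have the pathologist also record, on the same H&E sections, the tissue type next to the chip: viable tumour, necrosis, fibrosis or treated bed, or non-tumour. The form should separate a thin implant capsule, which section 1.3.15 shows as an expected reaction in mice (about 35 µm), from scar.

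**Section 7.1, Phase 1A.** Base the tumour-pO2 summary on chips confirmed in tumour, and show the all-subjects result beside it.

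**Section 7.1, Phase 1B.** Keep all subjects in the main summary. Annotate each with the tissue type and any existing imaging of chip position, and report pO2 with and without unconfirmed sites as a sensitivity analysis.

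**Feasibility endpoint.** Keep all sessions, wherever the chip lay.

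**Cost.** One extra field on an existing read and a somewhat smaller Phase 1A tumour-pO2 set. Two limits remain. Histology shows position only at removal, and it exists only where tissue is resected; section 5.2.4 foresees Phase 1B patients without definitive surgery and patients who die with the chip in place. If standard method 70.x already captures tissue type, only the section 7.1 rule is needed.

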### **5.3 Subject Compliance Monitoring**

Patients in Phase 1A will typically have the OxyChip implanted for a short duration ( $\leq 4$  weeks), but may remain for up to 52 weeks, and the patient will be seeing the surgeon for surgical planning and post-operative evaluations, making non-compliance unlikely. Phase 1A patients will be evaluated at least monthly prior to the OxyChip removal to check for any adverse events, as per the primary objective. Patients in Phase 1B will be receiving daily radiotherapy or a course of chemotherapy and therefore will be seen by a physician at least weekly or with each chemotherapy cycle for standard evaluation. At these appointments, the PI, co-investigators or staff protocol members perform safety monitoring by querying the patient about his or her local symptoms relating to the OxyChip implantation, and by inspection of the implantation site if possible, depending on the patient's willingness to allow inspection. Evaluation can also be performed at Norris Cotton Cancer Center North by one of the DH radiation or medical oncologists who are protocol staff, if the patients elects to receive radiation or chemotherapy at that facility prior to surgery (Phase 1B).

If the patient is unwilling to see the PI or co-investigators during a visit at which toxicity is to be assessed, or if the patient is unable to be seen due to logistical considerations, the patient by phone to evaluate potential toxicity. All efforts will be made to see the patient in clinic and perform an inspection of the implanted site. If the patient is receiving oxygen measurements, the patient will be seen by the EPR team at that time, ensuring compliance. It is possible that patients will decline oxygen measurements, but this will have a minor impact on the secondary objective (feasibility), and no impact on the primary objective (safety). Assessments by non-study physicians as part of standard of care are also an acceptable replacement if the patient is not accessible for an in-person evaluation.

#### **5.4 Prior and Concomitant Therapy**

- In Phase 1B, radiotherapy or chemotherapy or biologic or endocrine therapy will be delivered.
- All supportive medications are allowed on this protocol, including antibiotics, if needed.
- In Phase 1B, chemotherapy will not be given **with** radiotherapy (concurrently) or consecutively prior to surgical explantation of the tumor in this protocol.
- Angiogenesis inhibitors will not be given with radiotherapy in this protocol.
- Prior irradiation to the site where the OxyChip will be placed is not allowed.

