	
will still be eligible for enrollment as long as a PI or Co-PI on the study can evaluate the implanted site at least every two weeks during treatment. Of note, patients must receive their surgery at DH to be eligible.
 
 
• Superficial tumors located <math>\leq 3</math> cm from skin or mucosal surface, where neoadjuvant radiotherapy or neoadjuvant chemotherapy followed by surgical resection is planned.
 
• Eligible tumor histology for this protocol is any biopsy proven malignancy expected to undergo neoadjuvant chemotherapy or radiotherapy prior to resection
 
• Previous radiation to the site is not allowed.
 
• Use of angiogenesis inhibitors is not allowed.
 
• Planned use of concurrent neoadjuvant chemoradiotherapy, or sequential neoadjuvant radiation therapy and chemotherapy, prior to resection, is not allowed.
 
• Patients do not have to agree to an oxygen measurement in order to be eligible. Although oxygen measurements are desirable, the primary endpoint is safety of OxyChip during neoadjuvant radiation or chemotherapy.
 
• Tumors must be <math>\geq 2.5</math> cm in minimum diameter to be eligible.
 

OxyChip placement	Placement of OxyChip will be through a minimally invasive procedure ( see methods for implantation protocol ).
OxyChip removal	The OxyChip will be removed with the tumor mass at the time of surgical resection and examined for adverse events (primary goal). Tumor tissue surrounding the implanted device will be collected and stored to allow for future evaluation of molecular biomarkers (exploratory goal).
Oxygen measurements	The goal is at least two measurements prior to the start of radiation therapy and then up to five times per week during radiotherapy or chemotherapy for the secondary objective. Note, however, that oxygen measurements are not necessary for the study's primary goal to determine the presence or absence of any adverse events after implantation of the OxyChip.

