#### 5.2.4 OxyChip and Fiducial removal

The OxyChip and fiducial(s) will be excised with the surgical specimen. The surgeon determines the timing of surgery, but it will typically be planned to be within 4 weeks for Phase 1A, or after completion of radiotherapy or chemotherapy for Phase 1B, although the OxyChip may remain implanted for up to 52 weeks for both Phases (excluding the first 6 patients enrolled into Phase 1A). The minimum time from implantation to surgical excision required for inclusion is 3 days. Note, patients in Phase 1B are expected to have the OxyChip in place for a minimum of 5 weeks (the expected duration of radiation therapy). The protocol and goals for removal will be as follows:

- (i) All attempts will be made to maintain the OxyChip in the tissue specimen, without disrupting the shape or position within the tumor mass.
- (ii) In collaboration with the surgeon, after the patient has been anesthetized, imaging of the fiducial(s) will occur prior to surgery in order to identify the putative location of the OxyChip and facilitate surgical removal.
  - a. We anticipate the fluoroscopy will be sufficient for identification of the fiducial prior to surgical removal (and after). However, due to concerns that more advanced imaging may be necessary, the first three patients with fiducial implantation will have their surgery performed at DHMC in the Center for Surgical Innovation (CSI). If fluoroscopy is sufficient for identification, then subsequent surgeries can be performed in standard operating rooms as desired if fluoroscopy is available for identification of fiducials before and after surgery.
    - i. In the first three patients in the CSI, if the fiducial is not found prior to surgery either CT or MRI imaging will be performed to identify the fiducials. If the fiducials are found within the expected surgical field, or reasonably adjacent, fiducials will be removed during surgery. If the fiducials are found in an unanticipated area, consultation between the PI and the surgeon will occur as to whether surgical resection is acceptable. All decisions regarding surgery will be at the discretion of the surgeon. If no fiducials are found after advanced imaging prior to surgery, then surgery will proceed as planned as all reasonable measures will have been taken to identify the location of the OxyChip at that time.

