### **6.3 Post OxyChip implantation assessment (Phase 1A, 1B)**

1. Phase 1A patients will be evaluated at least monthly prior to OxyChip removal for assessment\* with respect to any adverse effects for the primary objective.
2. Phase 1B patients will be evaluated weekly during radiotherapy or prior to each chemotherapy administration or follow-up appointment for assessment\* of any adverse effects for the primary objective.

\* Assessments by non-study physicians or physician extenders as part of standard of care are acceptable. If a patient cannot or does not return for an evaluation, the study team will contact the patient by phone or email to assess for development of new adverse effects or changes in health status.

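### Phase 1B has no minimum interval for safety evaluations while the OxyChip is in place outside radiotherapy or chemotherapy; Phase 1A's monthly minimum could be extended to it at little cost

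*Combined protocol and SAP*

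**What the plan says.** Section 6.3 sets the adverse-effect evaluations for the primary objective. Item 1 reads "Phase 1A patients will be evaluated at least monthly prior to OxyChip removal". Item 2 reads "Phase 1B patients will be evaluated weekly during radiotherapy or prior to each chemotherapy administration or follow-up appointment". Section 3.1 repeats both rules. Section 5.3 gives the reasoning for Phase 1B: "Patients in Phase 1B will be receiving daily radiotherapy or a course of chemotherapy and therefore will be seen by a physician". It puts the frequency at once a week or more, or once per chemotherapy cycle.

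Four other provisions bear on Phase 1B time with the chip in place:

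- The Section 3.1 schema lets a patient have treatment at another hospital if an investigator can "evaluate the implanted site at least every two weeks during treatment".
- Section 6.4 has the site examined at each oxygen session, but the schema says "Patients do not have to agree to an oxygen measurement in order to be eligible".
- Section 6.5 requires one site check and one physical examination in the two weeks before surgery.
- Sections 3.1 and 6.3 provide phone or email contact for a patient who misses an evaluation, and accept standard-care assessments.

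Section 5.4 also says "In Phase 1B, radiotherapy or chemotherapy or biologic or endocrine therapy will be delivered". No evaluation rule mentions biologic or endocrine therapy.

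**The concern.** Each interval written for Phase 1B depends on treatment being given. Once radiotherapy or chemotherapy ends, only the follow-up appointment remains. The plan neither says how often one must occur nor requires that one be made. Phase 1A has no such hole, because its monthly rule runs until removal.

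The protocol itself foresees chip time outside treatment. The Study Summary expects implants of up to 12 weeks with radiotherapy, while Section 5.2.4 puts the radiotherapy course at 5 weeks. Section 1.6.2 gives a changed surgical schedule as a reason for longer residence. Section 5.2.4 also plans for surgery that proves unnecessary or is delayed past 52 weeks.

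At stake is how promptly and evenly local effects are found. Section 2.1 lists infection, inflammation and skin erosion at the site among the effects to monitor, and Section 8.2 has patients questioned at study visits. If no visit is due, no question is asked, and nothing triggers the phone or email contact.

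**Working it through.** The plan gives no figure to reproduce. The check compares the evaluation rules across periods and then does simple arithmetic for scale.

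**Coverage of Phase 1B implanted time**

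- During radiotherapy: weekly (6.3, 3.1, 5.3).
- During chemotherapy: before each administration (6.3, 3.1).
- Treated at another hospital: site check every two weeks, during treatment only (3.1 schema).
- Between implantation and the start of treatment: no interval. The schema aims for at least two oxygen measurements before radiotherapy, for patients who accept them.
- Between the end of treatment and surgery: no interval until the pre-operative examination (6.5).

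Over the same periods Phase 1A has the monthly minimum.

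**Inputs**

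- Radiotherapy course: 5 weeks (5.2.4).
- Expected implant with radiotherapy: up to 12 weeks (Study Summary). Ceiling: 52 weeks (3.1).
- One month taken as 30.4 days (365.25/12).

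**Formulas**

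- Weeks off radiotherapy = implant weeks − 5.
- Contacts under a monthly minimum = completed months in that time, taken as one continuous stretch.
- Required Phase 1B checks now = 5 weekly + 1 pre-operative.
- Phase 1A minimum over the same implant = completed months + 1 pre-operative.

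| Implant | Weeks off radiotherapy | Contacts under a monthly minimum | Phase 1B checks now | Phase 1A minimum |
|---|---|---|---|---|
| 12 weeks | 12 − 5 = 7 | 49/30.4 = 1.6, so 1 | 5 + 1 = 6 | 84/30.4 = 2.8, so 2 + 1 = 3 |
| 52 weeks | 52 − 5 = 47 | 329/30.4 = 10.8, so 10 | 5 + 1 = 6 | 364/30.4 = 11.97, so 11 + 1 = 12 |

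**Length of the unchecked stretch.** The pre-operative examination may fall up to two weeks before surgery. A continuous 7-week wait therefore leaves 5 to 7 weeks without a required check, and a 47-week wait leaves 45 to 47.

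**Number of checks by phase.** Phase 1A's minimum exceeds Phase 1B's 6 checks only once six months are complete: 6 × 30.4 = 182.4 days, or 182.4/7 = 26.1 weeks. At 12 weeks Phase 1B has twice as many required checks (6 against 3). They are concentrated in the treatment weeks.

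**Chemotherapy.** The Study Summary expects implants of 24 weeks or more, but the documents give neither the length of the chemotherapy nor the number of cycles. Off-treatment time cannot be computed for these patients.

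**Experience so far.** The longest human implant reported is 141 days (1.7), or 141/7 = 20.1 weeks.

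**The case against.** The strongest reply is that the plan does not rely on scheduled visits alone. Section 8.3.1.1 records adverse effects with a suspected link to the device whether observed or volunteered. Section 5.2.5 examines the tissue at the chip site histologically. Section 6.7 adds an evaluation 1 to 2 weeks after removal, and Section 4.4.1 allows early removal for an implant-related event. Section 1.7 promises close monitoring of the site, though without an interval. Section 3.1 lets oximetry continue up to removal. Oncology patients are seen often, and the worst toxicity grade reported in Section 1.5 is 1. The version history lists revised Phase 1B evaluation points for V8, so tying checks to clinic appointments looks deliberate.

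Most of this stands. A reader might infer that the primary endpoint and the stopping rule rest on scheduled checks alone. Sections 8.3.1.1 and 5.2.5 show that they do not, and a grade 3 event would probably come to attention anyway.

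A reader might also infer that Phase 1B is watched less than Phase 1A. At the expected 12-week radiotherapy implant the count runs the other way.

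A third tempting reading is that Section 5.4 admits patients on biologic or endocrine therapy alone, with no schedule at all. Section 4.1 and the schema name only neoadjuvant chemotherapy or radiotherapy, so such patients fall outside eligibility. Given alongside either treatment, the therapy is already covered by that treatment's checks.

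None of these points supplies a minimum interval for the wait before surgery.

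**Conclusion.** The point holds as a cheap improvement. Phase 1B evaluations have a set interval only during radiotherapy or around chemotherapy administrations. The rest of the implanted time lacks the minimum that Phase 1A has.

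At the expected radiotherapy implant the shortfall is about one contact. That assumes a 5-week course, a 12-week implant and off-treatment time in one stretch; split before and after radiotherapy, it could be less. The figure of about 10 contacts pairs a 5-week course with the 52-week ceiling and should be read only as an extreme upper bound. The documents do not say how many of the 30 Phase 1B patients will have a long off-treatment period.

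The benefit is earlier and more even detection of local effects. The documents do not support a claim that serious toxicity would go unrecorded.

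**What to change.** In Section 6.3 item 2, and in the matching text of Sections 3.1 and 5.3, add for Phase 1B: *and at least monthly from implantation until OxyChip removal whenever radiotherapy or chemotherapy is not being given*. State that inspection of the site is preferred, because phone or email cannot show early erosion or infection. Keep phone, email or standard-care assessment as the fallback that Section 6.3 already allows.

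The cost is one clause in three places and about one extra contact per patient at a 12-week radiotherapy implant, often met by a standard-care visit. Sample size, cohort expansion rules and analysis do not change.

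Separately, Section 5.4 should be reconciled with Section 4.1 by saying whether biologic or endocrine therapy is allowed only alongside neoadjuvant chemotherapy or radiotherapy. The clause above does not depend on the answer.
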